### **3.5.7.1.2 Serious Adverse Events**

An AE or suspected adverse reaction is considered "serious" (SAE) if, in the view of either the investigator or Sponsor, it results in any of the following outcomes:

- Death
- Life-threatening AE
- Inpatient hospitalization or prolongation of existing hospitalization
- Persistent or significant incapacity or substantial disruption of the ability to conduct normal life functions

- Congenital anomaly or birth defect
- Other medically important event

Important medical events that may not result in death, be life threatening, or require hospitalization may be considered serious when, based upon appropriate medical judgment, they may jeopardize the subject and may require medical or surgical intervention to prevent one of the outcomes listed in this definition. Examples of such medical events include allergic bronchospasm requiring intensive treatment in an emergency room or at home, blood dyscrasias or convulsions that do not result in inpatient hospitalization, or the development of drug dependency or drug abuse.

An AE or suspected adverse reaction is considered “life threatening” if, in the view of either the investigator or Sponsor, its occurrence places the subject at immediate risk of death. It does not include an AE or suspected adverse reaction that, had it occurred in a more severe form, might have caused death. The investigator must immediately (within 24 hours of awareness) report to the Sponsor any SAE through the agreed upon reporting mechanism.

### **3.5.7.1.3 Adverse Events of Special Interest**

Certain AESIs are evaluated after the administration of immunostimulatory agents. All subjects enrolled in the study will be monitored for AESIs from enrollment through the end-of-study (EOS) visit. The occurrence of any of these AEs will be treated as an SAE, meeting the criterion of a “medically important event.”

The list of AESIs is presented in [Section 6.2](#).

A diagnosis of an AESI will be reported to the Sponsor in an expedited manner similar to an SAE. The AESI diagnosis, as well as any medications taken to treat the condition, will be recorded in the subject’s eCRF.

### **3.5.7.1.4 Pregnancy**

The investigator is required to inform the Sponsor about any unexpected case of pregnancy occurring during the study (for female subjects), monitor the pregnancy until delivery, and report whatever outcome to the Sponsor (no later than 1 week after becoming aware of the pregnancy).

Pregnancy report forms will be distributed to the study site to be used for this purpose.

The investigator must immediately (within 24 hours of awareness) report to the Sponsor any case of pregnancy resulting in an abnormal outcome (miscarriage or newborn with congenital abnormality and/or stillbirth) according to the procedures described for SAEs.

### **3.5.7.2 Eliciting and Documenting Adverse Events**

The investigator is responsible for ensuring that all AEs and SAEs are recorded in the eCRF and reported to Moderna Therapeutics, Inc. In Part A of the study, AEs will be assessed from the time of the first dose administration at Visit 1 through Visit 7. However, for the time period after the ICF is signed until before receiving the study drug, AEs will only be recorded when they are defined as one or more of the following: SAEs, AESIs, or AEs leading to study withdrawal. In Part B of the study, AESIs and SAEs will be assessed from Visit 8 through Visit 19. Any AEs occurring before receipt of the study drug will be analyzed separately from TEAEs.

At every clinic visit or telephone contact, subjects will be asked a standard question to elicit any medically related changes in their well-being according to the scripts provided. Subjects will also be asked if they have been hospitalized, had any accidents, used any new medications, or changed concomitant medication regimens (both prescription and over-the-counter medications).

In addition to subject observations, data from clinical laboratory test results, physical examination findings, or other documents relevant to subject safety classified as an AE will be documented on the AE page of the eCRF.

### **3.5.7.3 Reporting Adverse Events**

All unsolicited AEs reported or observed during the study will be recorded on the AE page of the eCRF. Information to be collected includes drug treatment and dose, type of event, time of onset, investigator-specified assessment of severity and relationship to study drug, time of resolution of the event, seriousness, as well as any required treatment or evaluations, and outcome. The unsolicited AEs resulting from concurrent illnesses, reactions to concurrent illnesses, reactions to concurrent medications, or progression of disease states must also be reported. All AEs will be followed until they are resolved or stable or judged by the investigator to be not clinically significant. The MedDRA will be used to code all unsolicited AEs.

Any medical condition that is present at the time that the subject is screened but does not deteriorate should not be reported as an unsolicited AE. However, if it deteriorates at any time during the study, it should be recorded as an unsolicited AE.

Any AE considered serious by the investigator or which meets SAE criteria ([Section 3.5.7.1.2](#)) must be reported to the Sponsor immediately (within 24 hours of becoming aware of the SAE). The investigator will assess whether there is a reasonable possibility that the study drug caused the SAE. The Sponsor will be responsible for notifying the relevant regulatory authorities of any SAE as outlined in the 21 US Code of Federal Regulations (CFR) Parts 312 and 320. The investigator is responsible for notifying the institutional review board (IRB) directly.

The following contact information is to be used for SAE reporting:

SAE Hotline: PPD

SAE Fax line: PPD

### **3.5.7.4 Assessment of Severity of Unsolicited Adverse Events**

The severity (or intensity) of an AE refers to the extent to which it affects the subject's daily activities and will be classified as mild (Grade 1), moderate (Grade 2), severe (Grade 3), or potentially life threatening (Grade 4) using the following criteria:

- Mild (Grade 1): These events do not interfere with the subject's daily activities.
- Moderate (Grade 2): These events cause some interference with the subject's daily activities but do not require medical intervention.
- Severe (Grade 3): These events prevent the subject's daily activity and require medical intervention.
- Life threatening (Grade 4): These events require an emergency room visit or hospitalization.

Changes in the severity of an AE should be documented to allow an assessment of the duration of the event at each level of intensity to be performed. An AE characterized as intermittent requires documentation of onset and duration of each episode.

The Toxicity Grading Scale for Healthy Adult and Adolescent Volunteers Enrolled in Preventative Vaccine Clinical Trials ([CBER 2007](#)) will be used to categorize solicited

reactogenicity, safety laboratory test results, and vital sign measurements observed during this study. Specific criteria for clinical and laboratory abnormalities are presented in [Table 6-3](#) and [Table 6-4](#), respectively, and will be graded if outside of the reference range for the laboratory utilized. Of note, the laboratory test value itself may not be the AE classification. Each AE will be classified by its most specific term (eg, renal insufficiency, bronchitis) and supporting evidence (eg, laboratory test value, x-ray) will not be classified as an AE per se.

### **3.5.7.5 Assessment of Causality**

The investigator's assessment of an AE's relationship to study drug is part of the documentation process but is not a factor in determining what is or is not reported in the study.

The investigator will assess causality (ie, whether there is a reasonable possibility that the study drug caused the event) for all AEs and SAEs. The relationship will be characterized using the following classification:

- Not related: There is not a reasonable possibility of Sponsor's product relationship: Subject did not receive the Sponsor's product OR temporal sequence of the AE onset relative to administration of the Sponsor's product is not reasonable OR the AE is more likely explained by another cause than the Sponsor's product.
- Related: There is a reasonable possibility of Sponsor's product relationship: There is evidence of exposure to the Sponsor's product. The temporal sequence of the AE onset relative to the administration of the Sponsor's product is reasonable. The AE is more likely explained by the Sponsor's product than by another cause.

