### **3.3 Withdrawal of Subjects From the Study**

#### **3.3.1 Reasons for Withdrawal**

Subjects can withdraw consent and discontinue from the study at any time, for any reason, without prejudice to further treatment.

The investigator can also withdraw a subject, upon the request of Moderna Therapeutics, Inc. or if Moderna Therapeutics, Inc. terminates the study. Upon occurrence of a serious or intolerable AE, the investigator will confer with the Sponsor or designee. If a subject desires to withdraw from the study because of an AE, the investigator will try to obtain agreement to continue to follow that subject for that event only until it is resolved or until stable and then complete an EOS form. In the event of a safety concern that results in withholding from further vaccination, the subject will be continued in the trial for safety evaluations.

Every reasonable attempt will be made to follow subjects for safety throughout the entire trial period even if further vaccination is withheld or the subject misses visits. The reason for subject withdrawal or lost to follow-up will be documented.

The investigator, in consultation with the Sponsor's medical monitor, **may** withhold a subject **from further vaccination** if the subject experiences any of the following:

1. Becomes pregnant;
2. Develops, during the course of the study, symptoms or conditions listed in the exclusion criteria;

3. Experiences an AE (other than reactogenicity) after vaccination that is considered by the investigator to be possibly or probably related to treatment and is of Grade 3 (severe) or higher severity;
4. Experiences an AE or SAE that, in the judgment of the investigator, requires study drug withdrawal due to its nature, severity, or required treatment, regardless of the causal relationship to treatment;
5. Experiences a clinically significant change in clinical laboratory test results, vital signs, or general condition that, in the judgment of the investigator, requires treatment withdrawal;
6. Experiences anaphylaxis clearly attributed to study vaccine;
7. Experiences generalized urticaria related to the study vaccine.

The reason for withdrawing or refusing from further vaccination will be recorded. In addition, if a subject refused further vaccination they will be continued in the trial with all planned visits and assessments relative to the vaccination schedule and including visits through 1 year post final vaccination.

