### **3.4.2.2 Pause Rules**

During the active vaccination period, if any of the following events occur and are assessed to be potentially mRNA-1325 related, the cohort will be paused for further enrollment and vaccination, and an unscheduled SMC will be convened to assess specific data concerns and make recommendations:

- Two or more Grade 3 (or greater) reactogenicity events (whether systemic or local) within a dose cohort following any single (eg, the first, the second) vaccination
- Two or more Grade 3 (or greater) same laboratory toxicity score within a dose cohort
- One or more SAEs assessed as vaccine related, including any systemic hypersensitivity reaction

An unscheduled SMC may also be convened (with vaccination pausing if deemed necessary), by the investigator, IST, or Sponsor, if any other significant safety or tolerability issues are identified in the comprehensive review of available data that warrant further evaluation before additional subjects are dosed. This may include emerging non-clinical data, clinically relevant AEs, or relevant data from other sources indicating safety concerns even if the event(s) per se does not meet the criteria specified in this section.

Should a pause be triggered in the study, then each subject's visits will continue until the next scheduled vaccination visit. Should a pause affect a subject's vaccination visit, then the window for that subject's vaccination visit will be suspended until the pause is lifted and vaccination can resume. Once the pause is lifted at the site, vaccination should be reinstated as soon as possible. Visits should thereafter be scheduled as if they had received their second vaccination within the 28 (+7) day time window.

Should a pause be prolonged such that the second vaccination takes place outside the 28 (+7) day time window, the Sponsor has the option to add additional subjects in a dosing cohort to achieve the original number of subjects planned to be dosed within the 28 (+7) day time window. If a subject is in the screening period for more than 28 days as the result of a pause, they may be rescreened for study eligibility as long as they continue to provide consent to participate in the study.

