##### **3.5.7.1.1 Definitions**

An AE is defined as any untoward medical occurrence associated with the use of a drug in humans, whether or not considered drug related. Subjects will be instructed to record any AEs (solicited or unsolicited) in the memory aid.

A treatment-emergent AE (TEAE) is defined as any event not present before exposure to study drug or any event already present that worsens in intensity or frequency after exposure.

A suspected adverse reaction is any AE for which there is a reasonable possibility that the study drug caused the AE. For the purposes of investigational new drug safety reporting, “reasonable possibility” means that there is evidence to suggest a causal relationship between the study drug and the AE. A suspected adverse reaction implies a lesser degree of certainty about causality than adverse reaction, which means any AE caused by a study drug. An adverse reaction is any AE caused by a drug. Adverse reactions are a subset of all suspected adverse reactions for which there are reasons to conclude that the drug caused the event.

An AE or suspected adverse reaction is considered “unexpected” if it is not listed in the investigator’s brochure or at the specificity or severity that has been observed with the study drug being tested; or, if an investigator’s brochure is not required or available, is not consistent with the risk information described in the general investigational plan or elsewhere in the current application. For example, under this definition, hepatic necrosis would be unexpected (by virtue of greater severity) if the investigator’s brochure referred only to elevated hepatic

enzymes or hepatitis. Similarly, cerebral thromboembolism and cerebral vasculitis would be unexpected (by virtue of greater specificity) if the investigator's brochure listed only cerebral vascular accidents. "Unexpected," as used in this definition, also refers to AEs or suspected adverse reactions that are mentioned in the investigator's brochure as occurring with a class of drugs or as anticipated from the pharmacological properties of the drug, but are not specifically mentioned as occurring with the particular drug under investigation.

Unsolicited AEs will also be evaluated by the investigator for the coexistence of any of the other following conditions:

- Medically attended AE: an AE that leads to an unscheduled visit to a healthcare practitioner

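### The causality question asks for a reasonable possibility, but the recorded category turns on the likelier cause, so one AE can be both a suspected adverse reaction and 'Not related'; the withholding and pause rules use terms the recorded scale lacks

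*Protocol*

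**What the plan says.** Protocol section 3.5.7.1.1 (Definitions): "A suspected adverse reaction is any AE for which there is a reasonable possibility that the study drug caused the AE". For IND safety reporting, it explains that a reasonable possibility means "there is evidence to suggest a causal relationship between the study drug and the AE". It adds: "A suspected adverse reaction implies a lesser degree of certainty about causality than adverse reaction".

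Protocol section 3.5.7.5 (Assessment of Causality) has the investigator judge, for all AEs and SAEs, "whether there is a reasonable possibility that the study drug caused the event". The answer is recorded in two categories:
- 'Not related' lists conditions joined by OR. One of them is that "the AE is more likely explained by another cause than the Sponsor's product".
- 'Related' lists exposure, reasonable timing, and "The AE is more likely explained by the Sponsor's product than by another cause".

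Section 3.5.6 confirms that only these two levels are recorded. Section 3.5.7.3 puts the reasonable-possibility question again for SAEs.

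Two operating rules use other terms:
- Section 3.3.1, item 3, on withholding further vaccination, refers to AEs that the investigator considers "possibly or probably related to treatment".
- Section 3.4.2.2 opens by asking whether an event is potentially related to mRNA-1325. Its SAE bullet then reads "One or more SAEs assessed as vaccine related, including any systemic hypersensitivity reaction".

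Relatedness is used in the AE summaries (3.6.5.2) and in the data the Safety Monitoring Committee (SMC) sees before each escalation (3.4.2.1).

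**The concern.** One phrase carries two thresholds. Under 3.5.7.1.1, evidence pointing to the vaccine is enough. Under 3.5.7.5, the vaccine must also compare favourably with other explanations. An investigator who follows the category descriptions will file as 'Not related' some events that the protocol elsewhere calls suspected adverse reactions.

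This is a first-in-human trial whose primary objective is safety. The relationship tables and the relatedness column given to the SMC are among the summaries on which dose escalation is judged. The SAE pause trigger needs only one event assessed as vaccine related, so it matters which scale that assessment uses. The classification is made at the site under protocol wording, before any analysis, so a statistical analysis plan cannot repair it afterwards.

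**Working it through.** The plan states no figure to reproduce. The check sets the definitions side by side and asks how each would classify the same event.

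**Step 1: classify four kinds of AE.** In all four, exposure and timing are taken as compatible with a vaccine effect.

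| AE | Section 3.5.7.1.1 | Section 3.5.7.5 |
|---|---|---|
| Evidence of a vaccine role; vaccine the likelier cause | Suspected adverse reaction | Related |
| Evidence of a vaccine role; another cause likelier | Suspected adverse reaction | Not related |
| Evidence of a vaccine role; both equally likely | Suspected adverse reaction | Neither description is met |
| No evidence of a vaccine role; another cause likelier | Not a suspected adverse reaction | Not related |

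The sections agree on the first and last rows. The second row is a contradiction and the third is a gap.

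**Step 2: does this depend on how 'Related' is read?** One could treat its three sentences as considerations rather than joint requirements. The second row does not change, because the conditions for 'Not related' are joined by OR and a likelier alternative is sufficient alone.

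**Step 3: direction.** Let N be the number of AEs that meet the 3.5.7.1.1 meaning, and f the share of them in which the vaccine is also the likelier cause. Assume that an event whose leading explanation is the vaccine always carries some evidence of a vaccine role, and that ties are not filed as 'Related'. Then:

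- related under 3.5.7.1.1 = N
- related under 3.5.7.5 = f × N
- shortfall = (1 − f) × N

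Since f lies between 0 and 1, the 3.5.7.5 count can equal or fall below the other, but cannot exceed it. Filing ties as 'Related' shrinks the shortfall without reversing it.

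**Step 4: size.** The documents give neither N nor f. With f as a pure assumption, the relative shortfall 1 − f is 0% at f = 1, 25% at f = 0.75, 50% at f = 0.5 and 75% at f = 0.25. This range shows only that the size cannot be derived from the plan.

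**Step 5: terms in the operating rules.**

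| Place | Term for relatedness | On the recorded scale? |
|---|---|---|
| 3.5.6 and 3.5.7.5 | related / not related | Yes; this is the scale |
| 3.3.1, item 3 | possibly or probably | No |
| 3.4.2.2, lead-in | potentially | No |
| 3.4.2.2, SAE bullet | assessed as related | Perhaps; not stated to be the same judgement |

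The protocol does not map the lower three rows to the first. For an SAE, the lead-in and the bullet of the pause rule both apply and use different terms.

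**The case against.** Several points on the other side have force.

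- **Scope of the definition.** Section 3.5.7.1.1 gives its meaning for IND safety reporting, and its remark about lesser certainty compares a suspected adverse reaction with an established one, which does not exclude a likelier-cause standard. Both points are correct. The conflict therefore rests on the evidence wording alone. It survives because 3.5.7.3 and 3.5.7.5 use the same phrase for the investigator's judgement and no other definition is offered.
- **An even-odds test.** A reader might infer that every event at or below a 50% chance of being vaccine-caused is misclassified. The text does not say so. The test is comparative: if alternatives are weighed one at a time, a vaccine at 40% against two others at 30% each (40 + 30 + 30 = 100) is the leading cause and can be 'Related'.
- **The primary comparison.** A reader might infer that the safety comparison with placebo is biased. It is not affected. The endpoints in 3.6.1 are not restricted by relatedness, the comparison in 3.6.5.2 uses all AEs, and 3.5.7.5 states that causality does not decide what is reported. Blinded investigators also apply the same wording in both arms.
- **Safety backstops.** A reader might infer that one misfiled SAE prevents any pause. Section 3.4.2.2 lets the investigator, the internal safety team or the Sponsor convene the SMC, and pause if needed, when its criteria are not met. The SMC sees all unsolicited AEs before escalation, and every SAE goes to the Sponsor within 24 hours. Withholding under 3.3.1 is discretionary, and item 4 applies whatever the causal relationship. These routes stand. What remains unclear is the automatic SAE trigger, which does depend on relatedness.

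**Conclusion.** The inconsistency is real and does not depend on how the 'Related' description is parsed. An AE with evidence of a vaccine role but a likelier alternative receives opposite labels in 3.5.7.1.1 and 3.5.7.5, and a tie receives none in 3.5.7.5. The terms in 3.3.1 and 3.4.2.2 are not tied to the recorded scale.

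The consequence is limited. Related AEs can be under-counted in the by-relationship tables and in the relatedness data given to the SMC, and it is uncertain which judgement fires the automatic SAE pause. To say that related AEs are under-counted, as a fact or by some amount, goes further than the documents allow: the direction follows from Step 3 and its assumptions, but the shortfall could be nil. If the pause rule's own terms are judged separately from the 3.5.7.5 categories, that rule may not be weakened at all; the protocol does not say. The point is worth correcting because the trial is first-in-human and the correction is cheap.

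**What to change.** Reconcile sections 3.3.1, 3.4.2.2, 3.5.6, 3.5.7.1.1, 3.5.7.3 and 3.5.7.5 to one causality definition:

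1. Make the 'Related' and 'Not related' categories in 3.5.7.5 agree with the protocol's own meaning of reasonable possibility, and make them exhaustive so that an AE equally explained by the vaccine and another cause has a defined place.
2. State how the relatedness terms in 3.3.1 and 3.4.2.2 map to the recorded category, or say that they are separate judgements and where they are recorded. Resolve the difference between the pause rule's lead-in and its SAE bullet. Which threshold should govern withholding and pausing is a clinical choice for the sponsor; an explicit mapping prevents a change to the recorded category from altering those rules unnoticed.
3. Carry the same wording into the eCRF completion guidance.

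The cost is protocol and eCRF guidance wording, and possibly a slightly higher count of related AEs. No endpoint, sample size or all-cause analysis changes.
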